Maternal Two-year Follow-up	2 years of child's age	Medical history Blood pressure & anthropometric (height, weight, waist, hip) assessments Blood collection for lipid profile and additional analytes
Child Five-year Follow-up	5 years of age	Medical history, height and weight Cognitive, behavior, and vision test

Information on interventions during the pregnancy such as receipt of antenatal corticosteroids, tocolytics, or antihypertensive medications, pregnancy complications, and delivery outcomes will be collected by trained research personnel from chart review. Blood pressure measurements made during labor will be abstracted from the patient's chart. For the neonate, birth weight, length, head circumference, and ABR/OAE testing, will be obtained from the infant's chart. Neonatal data on all infants will be collected through discharge or 120 days after birth, whichever occurs first.

All patients will be followed up at 6 weeks postpartum, and information on any postpartum complications, including readmissions for blood pressure control, postpartum preeclampsia, infection or other morbidities, will be recorded.

The children will be followed for five years with study visits performed at 2 years and 5 years of age, including neonates who fail both the ABR and OAE testing at birth. To keep in touch with the family, follow-up coordinators will use a variety of methods, including contacting the family by telephone/e-mail/text every six months. Comprehensive pediatric neurodevelopmental testing will be performed at these two time points by study examiners that are trained and certified for the study. At the time of the 2-year child visit, maternal assessments will also be performed.

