4.6.3 Fetal and Neonatal secondary outcomes

1. Fetal and neonatal death
2. Birth weight and rate of “small for gestational age” as measured by birth weight: a) < 5 th percentile and b) < 10 th percentile for gestational age, assessed specifically by sex and race of the infant based on United States birth certificate data^{110,111}
3. Admission to neonatal intensive care unit/intermediate nursery and total length of stay in that unit
4. Complications of prematurity including:
 - a. Mechanical ventilation in the first 72 hours of life and duration
 - b. Oxygen support and duration

- c. Respiratory distress syndrome (RDS), defined as the presence of clinical signs of respiratory distress (tachypnea, retractions, flaring, grunting, or cyanosis), with an oxygen requirement and confirmed by a chest x-ray
- d. Bronchopulmonary dysplasia (BPD), defined as oxygen requirement at 28 days of life and at 36 weeks corrected gestational age
- e. Necrotizing enterocolitis (NEC), defined as modified Bell Stage 2 (clinical signs and symptoms with pneumatosis intestinalis on radiographs) or Stage 3 (advanced clinical signs and symptoms, pneumatosis, impending or proven intestinal perforation)
- f. Intraventricular hemorrhage (IVH) grade III-IV
- g. Periventricular leukomalacia (PVL), diagnosed by neuroimaging
- h. Retinopathy of prematurity (ROP) stage III or higher
 - i. Neonatal sepsis (within 72 hours and > 72 hours after birth). The diagnosis of sepsis will require the presence of a clinically ill infant in whom systemic infection is suspected with a positive blood, CSF, or catheterized/suprapubic urine culture; or, in the absence of positive cultures, clinical evidence of cardiovascular collapse or an unequivocal radiograph confirming infection.
 - j. Composite outcome of: fetal or neonatal death, RDS, Grade III-IV IVH, PVL, Stage 2 or 3 NEC, BPD, Stage III or higher ROP, or early onset sepsis
 - k. Seizures
- 5. Congenital anomaly / birth defect (excluding any conditions that must have been present before randomization)
- 6. Neonatal auditory brain stem response (ABR)/ Otoacoustic Emissions (OAE)

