4.7 Adverse Event Reporting

Detailed information concerning adverse events will be collected and evaluated throughout the conduct of the protocol.

Any maternal death, neonatal death, life threatening maternal event or Serious Adverse Event of Special Interest as defined in Section 4.5 must be entered into the adverse events database within twenty-four hours of being notified. If a death is reported, a copy of the patient's de-identified medical record will be uploaded to the adverse events database.

Adverse events which do not qualify under the above definition must be entered into the database within 7 days of being notified.

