6.2 Sample Size and Power

In all of the older studies, except the High Risk Aspirin study, aspirin was not being used routinely. In the High Risk Aspirin trial, the dose was lower than is generally used today and was started later in gestation. Therefore, for the purposes of sample size estimation, it is conservatively assumed that all women will be receiving low dose aspirin, and that the rate of preeclampsia (primary outcome) in the placebo group is 20%. It is estimated that a sample size of 1,550 women is required to demonstrate at least a 30% reduction in preeclampsia with the use of pravastatin (from 20% to 14%), with a power of 85%, and type I error of 5% 2-sided. The sample size is adjusted for a drop-out rate of 5% (i.e. that 5% of the women on pravastatin discontinued their study drug and had the same primary outcome rate as the placebo group) and for the interim 'looks' at 50% and 75% information.

Table 5. Sample Sizes for Different, Levels of Power and Effect Sizes

Reduction in Primary Outcome Rate	Power %	Estimated Sample Size
25%	80	2000
	85	2280
	90	2660
30%	80	1360
	85	1550
	90	1810
35%	80	980
	85	1120
	90	1290

Trials evaluating cardiovascular disease event rates have reported that the combination of pravastatin and aspirin consistently has greater efficacy than pravastatin or aspirin alone indicating at least an additive and possibly a synergistic effect.¹¹⁹ Therefore, there is minimal concern that concomitant aspirin use would reduce the effect size.

Preterm birth < 37 weeks of gestation is considered to be the major secondary outcome. With a sample size of 1550, there is more than 80% power to detect an effect as small a 20% reduction in preterm birth.

The sample size for this study is also sufficient to detect with at least 80% power a 40% reduction in preterm delivery < 34 weeks and a 30% reduction in NICU/special care admission.

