7.1 Data Collection Forms

Data will be collected on standardized forms on which nearly all responses have been pre-coded. Each form is briefly described below:

- Screening Log
- Eligibility and Randomization Form is completed for all patients eligible for the study.
- Study Drug Randomization Log: lists patients randomized to pravastatin or placebo, and provides the drug code number.
- Baseline Form is completed for all randomized patients. This form includes detailed demographic and social data, medical and obstetrical history, and current pregnancy complications.
- Previous Pregnancy Outcome Form
- Study Visit Form documents monthly study visits, possible side effects and compliance
- Creatine Kinase Log documents CK values reported for the participant.
- Study Drug Dispensing and Compliance Log documents the dispensing of study medication and the return of any unused study medication.
- Study Drug Alteration Log for Side Effects documents the modification of study medication due to side effects.
- Unscheduled Visit or Hospitalization Form is completed for all patients who had an unscheduled emergency room, Labor & Delivery, clinic visit or hospitalization between the scheduled monthly visits, including the delivery admission.
- Maternal Delivery and Outcome Form documents specific pregnancy complications since randomization, in addition to labor, delivery and postpartum information.
- Neonatal Baseline Form records date and time of birth, delivery data and status at delivery, for each fetus/infant.
- Neonatal Outcome Form records outcome data for all infants admitted to the NICU or special care nursery.
- Patient Status Form documents loss to follow up/withdrawal status, last date of contact for lost to follow-up patients, side effects since the last dose.
- Follow-up Visit Form documents maternal complications since discharge and the 6-week postpartum study visit.
- Postpartum Readmissions Log is completed for all patients who are readmitted to the hospital after discharge following delivery.
- Adverse Event Form records serious and non-serious adverse events.
- Outcome Diagnosis Form records outcome data for hypertension and preeclampsia
- Two Year Study Visit Form for infants and proprietary forms for neurodevelopmental and behavior testing

- Five Year Study Visit Form for infants and proprietary forms for neurodevelopmental and behavior testing

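### Neonatal follow-up ends at discharge with no fixed horizon, so if pravastatin shortens stay or NICU use, late neonatal events would be under-counted more in that arm

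*Combined protocol and SAP*

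**What the plan says.** Section 4.4 sets the neonatal window: "Neonatal data on all infants will be collected through discharge or 120 days after birth, whichever occurs first". No fixed horizon, such as day 28, is given anywhere.

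Section 4.6.3 lists outcomes that can first appear after a routine discharge, without an upper age: "Neonatal sepsis (within 72 hours and > 72 hours after birth"), "Fetal and neonatal death", seizures, and congenital anomalies (other than those that must pre-date randomization). Length of stay in the NICU or intermediate nursery is itself an outcome in the same list.

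On forms, Section 7.1 says: "Neonatal Outcome Form records outcome data for all infants admitted to the NICU or special care nursery". The other newborn form covers birth, delivery and status at delivery. For the 6-week contact: "Follow-up Visit Form documents maternal complications since discharge and the 6-week postpartum study visit".

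Other routes exist. Table 4 and Appendix A include an adverse-event review at 6 weeks. Section 4.7 says: "Detailed information concerning adverse events will be collected and evaluated throughout the conduct of the protocol". It also requires entry within 24 hours of notification for the following: "Any maternal death, neonatal death, life threatening maternal event or Serious Adverse Event of Special Interest as defined in Section 4.5". Section 4.4 adds family contact every six months and child visits at 2 and 5 years, which include a medical history.

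Section 6.3 does not mention unequal neonatal observation.

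**The concern.** The window closes on an event that follows randomization and that treatment may influence. An infant who goes home from the routine nursery leaves observation early, while one in the NICU stays under observation until discharge or the 120-day cap. Section 3.2 asks whether pravastatin prolongs gestation and alters neonatal morbidity, and Section 6.2 claims power for "a 30% reduction in NICU/special care admission". If those hopes are met, pravastatin infants are observed for less time on average.

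Events that begin or are recognised after discharge would then be missed more often in the pravastatin arm. Equal true risks could look favourable, and a real increase could look smaller than it is. Section 2.5 records that the package insert still contraindicates the drug in pregnancy, so infant safety comparisons should not depend on length of stay.

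**Working it through.** **1. The plan's own figure.** Section 6.2 claims at least 80% power for a 30% reduction in NICU/special-care admission but gives no base rate. With 1,550 / 2 = 775 women per arm and a two-sided 5% comparison of proportions, power is about 76% at a base rate of 15%, 88% at 20% and 98% at 30%. The claim therefore fits a base rate of 20% or 30%, and both are used below as assumptions. The 30% is an effect the trial could detect, not one the plan predicts.

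**2. Direction in the pilot (Table 2).** NICU stay of at least 48 hours: 8/20 placebo versus 4/20 pravastatin (Fisher p = 0.30). Routine nursery as highest level of care: 9/20 versus 14/20 (p = 0.20). Gestational age at delivery: +1.5 weeks (-0.4 to 3.3). All point toward shorter stay; none is significant.

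**3. Model.** Let p_T and p_C be the proportions admitted on pravastatin and placebo, r the late-event risk in admitted relative to non-admitted infants, and c the share of late events in non-admitted infants that still reaches the database. Treatment acts only through admission, and events in admitted infants are taken as fully captured.

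- True RR = [p_T·r + (1 − p_T)] / [p_C·r + (1 − p_C)]
- Recorded RR = [p_T·r + (1 − p_T)·c] / [p_C·r + (1 − p_C)·c]
- Distortion = recorded / true

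Dividing by the true RR keeps a genuine fall in events, due to fewer admissions, out of the bias. Neither r nor c is in the documents.

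| Admitted, placebo vs pravastatin | r | c | True RR | Recorded RR | Distortion |
|---|---|---|---|---|---|
| 30% vs 21% | 1 | 0 | 1.00 | 0.21/0.30 = 0.70 | 0.70 |
| 30% vs 21% | 1 | 0.5 | 1.00 | 0.605/0.65 = 0.93 | 0.93 |
| 30% vs 21% | 10 | 0 | 2.89/3.70 = 0.78 | 2.10/3.00 = 0.70 | 0.90 |
| 30% vs 21% | 10 | 0.5 | 0.78 | 2.495/3.35 = 0.74 | 0.95 |
| 20% vs 14% | 1 | 0.5 | 1.00 | 0.57/0.60 = 0.95 | 0.95 |
| 20% vs 14% | 10 | 0 | 2.26/2.80 = 0.81 | 1.40/2.00 = 0.70 | 0.87 |
| 20% vs 14% | 10 | 0.5 | 0.81 | 1.83/2.40 = 0.76 | 0.94 |

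If admission is unchanged, the distortion is 1.00. If it rises from 30% to 36%, with r = 1 and c = 0.5, it is (0.36 + 0.32)/0.65 = 1.05, against pravastatin.

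**4. Masking of harm.** Now let capture be incomplete in both groups: assume 70% of events in admitted and 10% in non-admitted infants fall before discharge, with equal risk. At 30% versus 21% admitted, the capture ratio is (0.21 × 0.7 + 0.79 × 0.1)/(0.30 × 0.7 + 0.70 × 0.1) = 0.226/0.280 = 0.81. A true RR of 1.5 then reads 1.5 × 0.81 = 1.21. With no change in admission it reads 1.50; at 30% versus 36% it reads 1.69.

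**5. Which outcomes are exposed.** Late sepsis, seizures and late-recognised anomalies are exposed, and neonatal death in part. The neonatal stopping event in Section 5.4.3 is a failed newborn hearing test, a result Section 4.4 takes from the infant's chart and one obtained before discharge in the pilot (Section 2.5.3.2). The composite in Section 4.6.3 counts early-onset sepsis only, and its other non-death components are mostly inpatient diagnoses.

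**The case against.** The strongest reply is that the protocol does not confine infant safety to the hospital stay. Adverse events are collected throughout, they are reviewed at 6 weeks, neonatal death has its own expedited route with no discharge limit, and the child is seen at 2 and 5 years. Section 7.1 describes its forms only briefly, and a manual of operations that is not available here may hold more. This stands in part: capture after discharge is unlikely to be zero. But no route states that anyone asks about the infant's events in the neonatal period. Death reporting depends on notification, the six-monthly contact is there to keep in touch, and a 2-year history relies on late recall.

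A second reply is that late sepsis is listed among complications of prematurity, so equal risk in NICU and well infants is implausible and part of any recorded fall would be real benefit. That stands, and it is why the 0.70 figure is only a limiting case. Anomalies are also a narrow category, since treatment starts after organogenesis and conditions that must pre-date randomization are excluded.

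A reader might go further and infer that treatment does shorten stay, so that the safety results are biased toward pravastatin. That is the trial's hypothesis; the pilot differences are not significant. A reader might also infer that the hearing stopping rule, or the dose recommendation after 50 or 310 deliveries, would be misled. The hearing event is a newborn test, and with about 25 women per arm at the first review, a distortion of this size in rare late events would hardly register.

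**Conclusion.** The point holds in a conditional form. As written, ascertainment of late sepsis, seizures, late-recognised anomalies and part of neonatal death is tied to length of stay. If pravastatin shortens stay or reduces NICU use, the relative risk for these outcomes is pulled toward apparent benefit and a harm could be partly hidden; the other two cases give no bias or the opposite bias.

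The documents give no stay lengths, admission rates or post-discharge event rates, so the size is illustrative. With admission cut by 30% from an assumed 20% or 30%, the more plausible rows give a distortion of about 0.87 to 0.95; 0.70 needs both equal risk and no capture after discharge. This is a weakness in how secondary safety outcomes are ascertained, not a demonstrated bias. It does not touch the primary outcome and leaves the hearing rule and most of the composite largely intact. It is worth correcting because the remedy is cheap.

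**What to change.** At the existing 6-week visit, and on the Follow-up Visit Form, record for every infant: vital status to day 28, readmission, sepsis, seizures, and any anomaly diagnosed since birth. State in Sections 4.6.3 and 6.3 that neonatal death, late sepsis, seizures and anomalies are analysed on one fixed horizon for all infants, whether or not discharged: for example 28 days, or up to the 6-week visit for anomalies. Keep in-hospital collection to 120 days for the complications of prematurity. Under a common horizon with complete answers, the distortion is 1.00 whatever treatment does to stay.

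The cost is a few questions at a visit that already takes place, one form revision and a protocol amendment, which under Section 1.3 needs Steering Committee and IRB approval and submission to the IND. The downside is that some information will come from the mother and need confirmation from records.

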4.4.1 Child 2-year Follow-up

The following assessments will be performed at the child 2-year visit:

- Medical history including hearing loss and need of hearing aids
- Height and weight
- Cognitive, Motor and Language Scores from the Bayley Scales of Infant and Toddler Development 4
- The Gross Motor Function Classification System (GMFCS) and the Manual Abilities Classification System (MACS)
- Visual and hearing assessment
- Child Behavior Checklist (CBCL)

4.4.2 Maternal 2-year Follow-up

The following assessments will be performed at the same time as the child 2-year visit:

- Medical history
- Blood pressure

- Anthropometrics including height, weight, waist and hip circumferences
- Blood collection

Maternal blood will be processed for lipids, HbA1c, fasting glucose and insulin, hs-CRP, Lipoprotein A and other analytes.

4.4.3 Child 5-year Follow-up

The following assessments will be performed at the child 5-year visit:

- Medical history including hearing loss and need of hearing aids
- Height and weight
- Differential Ability Scales-II (DAS-II) cognitive assessment. The DAS II general conceptual ability score correlates well with full scale IQ as measured by the Wechsler Preschool and Primary Scale of Intelligence (0.89).
- Behavior Rating Inventory of Executive Function (BRIEF 2nd Edition)
- Vineland Adaptive Behavior Scales, 3rd Edition
- The Gross Motor Function Classification System (GMFCS) and the Manual Abilities Classification System (MACS)
- Child Behavior Checklist (CBCL)
- Ophthalmologic exam including visual acuity/refraction and cover test (evaluate strabismus)

4.5 Patient Management

Use of low dose aspirin is recommended, as it is currently standard of care in the U.S. for women with prior preeclampsia according to the ACOG guidelines.

Patients' pregnancy management (including antenatal testing, ultrasounds, control of hypertension, inpatient vs. outpatient management, and mode and timing of delivery) will be performed as recommended by standard prenatal care as defined by the respective participating institution. Inpatient vs. outpatient management of patients with preeclampsia (without severe features), single vs. double courses of antenatal corticosteroids in the setting of preterm labor, and other obstetric interventions will be left to the discretion of the treating physician.

Although chronic use of the drugs that may have potential significant interactions with pravastatin are listed as an exclusion criteria, the occasion may arise that a pregnant woman in the study may require one or more of these medications. Therefore, and to avoid any potential (or unknown) interactions; patients and providers in this study will be advised of the following:

- Study drug should be taken at least 1 hour before or 4 hours after the administration of cholestyramine.
- Cimetidine (H2-receptor antagonists) should be taken at least 1 hour before study drug.
- There is no need to change the timing or stop study drug if also taking aspirin, digoxin, or diltiazem.
- In the event that a patient requires erythromycin (e.g., rupture of membranes), an alternative antibiotic will be recommended if available. If not, the study drug will be stopped for the duration of erythromycin intake (usually 7 days). The study drug will be resumed at the end of that period.

In this study, the following events that could be related to pravastatin use will be defined and monitored as Adverse Events of Special Interest (AESI).

- Myalgia: diffuse muscle pain, cramps, or soreness without elevation in CK
- Muscle weakness: muscle weakness documented on physical exam without elevation in CK
- Myositis: muscle symptoms (myalgia or weakness) with CK elevations between 3 and 10 times upper limit of normal (ULN) in pregnancy or between 3 and 10 times the baseline CK value, whichever is higher
- Myopathy: muscle symptoms (myalgia or weakness) plus CK $\geq 10x$ ULN or 10x baseline CK
- Rhabdomyolysis: muscle symptoms (myalgia or weakness) plus CK $\geq 10x$ ULN or 10x baseline CK plus an elevation in serum creatinine (usually with brown urine and myoglobinuria) or need for medical interventions such as hospitalization and intravenous hydration.¹⁰⁴⁻¹⁰⁹
- Serious liver injury defined as persistent AST or ALT of 3 x ULN or increased AST or ALT levels with clinical symptoms and hyperbilirubinemia or jaundice, in the absence of severe preeclampsia or other hepatic disease

Severe Adverse Events of Special Interest will be defined as maternal myositis, myopathy, rhabdomyolysis, or serious liver injury. Patients will be advised throughout the study to report promptly unexplained muscle pain, tenderness or weakness, particularly if accompanied by malaise or fever. If myositis, myopathy, rhabdomyolysis, or serious liver injury occurs, the study drug (regardless of actual treatment assignment) will be discontinued permanently. If a patient develops myalgia or muscle weakness (documented on physical exam) with CK elevation $<3x$ ULN (or baseline CK), then the following will take place, 1) study drug will be stopped temporarily, 2) a workup will be done to ensure the patient does not have any of the other more serious muscle related serious adverse events, and 3) risk and precipitating factors will be evaluated. The patient will be monitored until complete resolution of symptoms and the CK values are back to normal (if applicable). The CK values will be checked weekly if above the ULN or baseline CK. Upon resolution, the patient will be re-challenged with pravastatin to be used every day or every other day.

Any woman who withdraws from taking study medication for any reason, including discontinuation for side effects, will be encouraged to continue study visits as planned, including the postpartum contact and follow-up of the child through 5 years of age.

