5.4.3 Trial Stopping Rules

For the primary outcome, the group sequential method of Lan and DeMets will be used to characterize the rate at which the type I error is spent.¹¹² This method is flexible with regard to the timing of the interim analyses. Asymmetric stopping boundaries will be used. The upper boundary which describes the stopping rule for benefit will be based on 1-sided type I error of .025 and the Lan-DeMets generalization of the O'Brien-Fleming boundary. The lower boundary will be based on a less stringent stopping rule: 1-sided type I error of .05 and the Lan-DeMets generalization of the Pocock type boundary.

It is also planned to calculate conditional power given the observed data to date, and conditional on the future data showing the originally assumed design effect. If this conditional power is low (under 10 percent) the DSMC may consider termination for futility if the accrual rate is slow, with confidence that the Type II error is not greatly inflated.¹¹³

Specific stopping rules for the trial will be established for monitoring maternal, neonatal and child events relevant to pravastatin risk. For the maternal stopping rule, an occurrence of one of the following events will qualify:

- Serious Adverse Event of Special Interest (serious AESI; myositis, myopathy, rhabdomyolysis or serious liver injury as defined in Section 4.5).
- Non-serious AESI (myalgia or muscle weakness as defined in Section 4.5) that required repeat discontinuation of study medication (initial discontinuation, rechallenge, discontinuation again)

For the neonatal stopping rule the following event will qualify:

- Failed newborn ABR/OAE test

The BCC will continuously monitor these maternal and neonatal events and if there is an excess of women in the pravastatin group who have experienced one or more of the events such that the one sided nominal p-value of a Fisher's exact test is less than 0.05 or such that the lower 90% confidence bound of the relative risk exceeds 1.0 for larger sample sizes of 50 or more, will request that the DSMC review the

data immediately and make a determination on stopping or pausing the trial, or modifying the dose. Likewise if there is an excess of neonates who have failed their hearing tests, the same stopping criteria will apply.

For the child stopping rule, the following events will qualify:

- Cognitive or Motor Scale Score < 70 (2.5th percentile) from the Bayley Certified Scales of Infant Development 4 at 24 months age

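### Section 4.5 defines the non-serious muscle events as having no CK elevation, so the Section 5.4.3 trigger, read literally, omits women stopped twice with CK raised but below 3x ULN

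*Combined protocol and SAP*

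**What the plan says.** Section 4.5 (Patient Management) lists the adverse events of special interest (AESI). The two non-serious muscle classes both require that CK is not raised: "Myalgia: diffuse muscle pain, cramps, or soreness without elevation in CK" and "Muscle weakness: muscle weakness documented on physical exam without elevation in CK". The next class up, myositis, is "muscle symptoms (myalgia or weakness) with CK elevations between 3 and 10 times upper limit of normal (ULN) in pregnancy", or the same multiples of the baseline value, whichever is higher. Myopathy and rhabdomyolysis start at 10x ULN or 10x baseline.

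Further on, Section 4.5 sets out what to do short of permanent discontinuation. The paragraph opens "If a patient develops myalgia or muscle weakness (documented on physical exam) with CK elevation" and sets the limit at below 3x ULN (or baseline CK). The drug is stopped temporarily, a work-up is done, and the woman is re-challenged once the episode resolves. On monitoring it adds: "The CK values will be checked weekly if above the ULN or baseline CK".

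Section 5.4.3 (Trial Stopping Rules) counts two kinds of maternal event. One is any serious AESI. The other is "Non-serious AESI (myalgia or muscle weakness as defined in Section 4.5) that required repeat discontinuation of study medication", meaning a stop, a re-challenge and a second stop. The coordinating center asks the DSMC for immediate review if the pravastatin excess gives a one-sided Fisher p below 0.05, or is "such that the lower 90% confidence bound of the relative risk exceeds 1.0 for larger sample sizes of 50 or more".

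Maternal secondary outcome 10 (Section 4.6.2) counts myalgia, muscle weakness and the serious AESI. It does not cite Section 4.5, but those terms are defined nowhere else.

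**The concern.** The protocol expects women with muscle symptoms and modestly raised CK, and it manages them, but it gives them no AESI class. Because 5.4.3 points to the 4.5 definitions, a literal reading counts a woman with normal CK who is stopped twice and omits a woman at, say, 2x ULN who is stopped twice. For a muscle-toxicity rule that ordering is backwards.

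Two things are at stake: whether a woman counts towards the maternal trigger for DSMC review, and whether she appears in secondary outcome 10. The second gap is wider, because that outcome needs no repeat discontinuation and so misses every symptomatic episode in the band. Efficacy analyses are not touched.

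**Working it through.** The plan states no figure for this point, so the check is mainly to set the rules side by side.

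**Step 1. Literal classification of a woman with muscle symptoms**

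| CK | AESI class (4.5) | Management (4.5) | Counts in 5.4.3? | Outcome 10? |
|---|---|---|---|---|
| Not raised | Myalgia or muscle weakness | Re-challenge text not worded for her | Yes, if stopped twice | Yes |
| Raised, below 3x | None | Stop, work-up, re-challenge | No, even if stopped twice | No |
| 3x to 10x | Myositis | Permanent stop | Yes, serious AESI | Yes |
| 10x or more | Myopathy or rhabdomyolysis | Permanent stop | Yes, serious AESI | Yes |

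The second row is the gap. Here 3x means 3x ULN or 3x baseline, whichever is higher. The gap concerns the episode: the same woman would still count if another episode met a listed class.

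One boundary detail matters for the fix. The myopathy line says 10x ULN or 10x baseline, without the whichever-is-higher condition. If baseline CK were 0.25x ULN (an illustrative value), 10x baseline would be 10 × 0.25 = 2.5x ULN, which is below 3x ULN. Such a woman could literally meet the myopathy definition while in the second row, so a repaired definition has to exclude anyone who already meets a serious class.

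**Step 2. How sensitive the trigger is to one woman**

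Inputs: 155 women per arm (the first 310 of Section 5.4.2, assuming an equal split); a = pravastatin women and b = placebo women with any qualifying maternal event; n = 155. The protocol does not name the interval method. I assume a Wald bound on the log relative risk with z = 1.645:

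lower bound = (a/b) × exp(−z × √(1/a − 1/n + 1/b − 1/n))

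- 6 v 1: √(1/6 + 1 − 2/155) = 1.074; 6 × exp(−1.645 × 1.074) = 1.03. Trigger met (Fisher p = 0.060, so through the bound).
- 5 v 1: √(1/5 + 1 − 2/155) = 1.090; 5 × exp(−1.645 × 1.090) = 0.83. Not met (Fisher p = 0.107).

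If the 90% bound is one-sided (z = 1.282), the edge moves by one: 5 v 1 gives 1.24 (met) and 4 v 1 gives 0.96 (not met).

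With no placebo events the result depends on how the rule is read. At 5 v 0 the Fisher p is 0.030, so the trigger is met if Fisher still applies at 50 or more. If only the bound applies there, adding 0.5 to each cell gives 11 × exp(−1.645 × √(1/5.5 + 1/0.5 − 2/155.5)) = 0.976, and the trigger is not met.

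**Step 3. What this does and does not show**

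Near its edge the trigger can turn on one woman. That holds for any rule based on small counts, and the counts include serious AESI, which the gap does not affect. The documents give neither the share of symptomatic women with CK between normal and 3x ULN nor a second-stop rate, so the number omitted cannot be estimated. The gap is the same in both arms, so omitting a placebo woman could also bring the trigger closer.

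**The case against.** The best defense is to read Section 4.5 as a whole. Its re-challenge paragraph itself uses the terms myalgia and muscle weakness for women with raised CK, and the myositis, myopathy and rhabdomyolysis definitions use them as plain symptom words. The sequence in 5.4.3 matches the only muscle-symptom re-challenge procedure in the protocol, so the authors surely meant the trigger to count women who go through it. The requirement that CK return to normal only where applicable suggests that women with normal CK were meant to follow the pathway too. This stands as evidence of intent. It does not remove the conflict, because 5.4.3 points to a definition and the definition excludes raised CK.

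A reader might infer that sites will code these women differently. The documents do not show that. The coordinating center monitors the trigger events centrally and reviews reports for completeness, and a masked medical monitor reviews classification of seriousness, unexpectedness and relatedness (5.3, 5.4.3). A manual of operations, not available here, may settle the coding.

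A reader might also infer that muscle toxicity would escape notice. That is not supported either. These women remain in adverse event reporting (4.7, 5.3). The DSMC sees adverse events, compliance and side effects by arm (5.4.1), and there are special safety reviews after 50 and 310 deliveries (5.4.2).

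**Conclusion.** The inconsistency is real and minor. Read literally, 4.5 and 5.4.3 together leave symptomatic women with CK raised but below 3x, stopped twice, out of the maternal trigger, and leave all symptomatic episodes in that band out of secondary outcome 10. The second part rests on 4.5 being the only place where the terms are defined.

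The size of the gap is unknown. The 6 v 1 and 5 v 1 comparison (bounds 1.03 and 0.83) shows how sensitive the rule is, under an assumed Wald bound with z = 1.645 and equal arms. It should not be read as the effect of the gap. The 5 v 0 case should be cited only with its condition that Fisher still applies at 50 or more. Nothing here supports a claim that the trigger would miss, or falsely raise, a signal in this trial. It only requests a DSMC review, and 5.4.3 says that stopping would not be decided on statistical grounds alone.

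**What to change.** In both Section 4.5 definitions (myalgia and muscle weakness), replace the condition that CK is not raised with: CK normal or below 3x ULN (or 3x baseline, whichever is higher), and not meeting a serious AESI definition. The first part joins the non-serious classes to the myositis threshold. The second prevents overlap with the 10x-baseline criterion described above.

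Sections 5.4.3 and 4.6.2 need no edit, since one cites the 4.5 definitions and the other uses the same terms. The trigger thresholds, the re-challenge schedule and the repeat-discontinuation requirement stay as they are.

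The cost is two edited lines through the usual amendment route. No new visits, tests or patients are needed, because the Creatine Kinase Log and the Study Drug Alteration Log (Section 7.1) already hold the relevant data. The downside is that a few more events may be counted, in either arm.
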